Corrected calcium	Eve dise	ery 4 we ease pro	eeks fro ogressic t	om the on, rega herapy	date of the fi ardless of who or subsequen	rst dose of stud ether the subjec nt therapy.	y drug until t is on study	Serum calcium and albumin from peripheral blood at D1 of each cycle until disease progression, even if subject is on subsequent therapy; if used as criterion for disease progression, must be confirmed by second value.	
Skeletal Imaging				If	clinically ind	cated			
CT/MRI assessment				As	clinically ind	icated			

Table 5.1-3: CA204142 Cycles 3 and Beyond - EPd Cohort and Cross-over Patients from EN Cohort

Procedure	Day 1	Day 8	Day 15	Day 22	Rest Days 23 - 28	End of Treatment	Days 30 & 60 post end of treatment*	Notes
Response per IMWG uniform criteria	Every until p dos shoul	4 week rogress se withi d still t	cs from sion. (C in a cyc be done	date o ycles c le is de on Da	f first dose of annot be dela alayed or omi y 1 of the cyc until dosing.	study drug on yed. In the eve itted, the tumor ele and should n .).	Cycle 1 Day 1 nt that the first assessment not be delayed	Subjects who discontinue from study treatment for reasons other than progression will continue to have tumor assessment every 4 weeks from C1D1 until progression. Following disease progression, subjects will be followed at least annually for survival.

* Subjects in the EN cohort who cross-over to the EPd cohort but discontinue treatment within 2 cycles of EPd treatment will still need to undergo 100 day followup visit from last dose of nivolumab to evaluate safety events related to study treatment.

Table 5.1-4:CA204142 Cycles 1 and 2 - EN Cohort

Procedure	Day 1	Day 8	Day 15	Day 22	Rest Days 23 – 28	Notes
Safety Assessments						
Targeted Physical Examination	Х					Perform prior to dosing, include weight
Vital Signs	Х	X	Х	X		Cycle 1: Measure vital signs pre-elotuzumab infusion, 30 minutes after the start of elotuzumab infusion, at the end of infusion, and 30 minutes after the completion of infusionCycle 2 and beyond: Evaluate prior to dosing.Vital signs must be collected if infusion related AE occurs.
Performance Status (ECOG)	Х					Evaluate prior to dosing
Serious Adverse Event Assessment	Х	X	Х	X		Evaluate prior to dosing
Adverse Events Assessment	Х	Х	Х	X		Evaluate prior to dosing
Concomitant Medications	Х	X	Х	X		Evaluate prior to dosing
Second Primary Malignancy	Х					
Laboratory Tests						

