Response per IMWG uniform criteria	Every drug on cannot within assessr cycle a	4 weeks Cycle 1 be delay a cycle nent sho and shou	s from da Day 1 u ed. In the is delaye ould still l ild not be	te of firs ntil prog e event t d or om be done e delayed	st dose of study gression. (Cycles hat the first dose itted, the tumor on Day 1 of the d until dosing.).	Subjects who discontinue from study treatment for reasons other than progression will continue to have tumor assessment every 4 weeks from C1D1 until progression. Response assessments and PD require confirmation (2 consecutive assessments made at any time) before the institution of any new therapy.					

Table 5.1-4:CA204142 Cycles 1 and 2 - EN Cohort

Procedure	Day 1	Day 8	Day 15	Day 22	Rest Days 23 – 28	Notes

Table 5.1-5:CA204142 Cycles 3 and 4 - EN Cohort

Procedure	Day 1	Day 8	Day 15	Day 22	Rest Days 23 – 28	Notes						
Safety Assessments												
Targeted Physical Examination	Х					Perform prior to dosing, include weight						
Vital Signs	Х		Х			Evaluate prior to dosing.						
Performance Status (ECOG)	Х					Evaluate prior to dosing						
Serious Adverse Event Assessment	Х		Х			Evaluate prior to dosing						
Adverse Events Assessment	Х		Х			Evaluate prior to dosing						
Concomitant Medications	Х		Х			Evaluate prior to dosing						
Second Primary Malignancy	Х											
Laboratory Tests												
CBC, differential, platelets	Х					Can be drawn up to 3 days prior to study visit (See Section 5.3.4).						
Chemistry	Х					Can be drawn up to 3 days prior to study visit						
Pregnancy Test	Х					For WOCBP only. Urine tests must have a sensitivity of at least 25 IU/L. Test within 24 hours.						

Table 5.1-5:CA204142 Cycles 3 and 4 - EN Cohort

Procedure	Day 1	Day 8	Day 15	Day 22	Rest Days 23 – 28	Notes		
Thyroid stimulating hormone (TSH) (reflex to free T3/total T3, free T4 for abnormal TSH result).	Х*					To be performed every *2 cycles (± 7 days) from first dose regardless of dosing schedule.		
Efficacy Assessme	ents							
Myeloma Urine		(0	Central Lab A	Analysis)		Day 1 of each cycle (See also: Section 5.4.2)		
and Serum Lab tests (SPEP/UPEP/sF LC/Igs)	Every 4 disease	weeks from progressic study the	n date of firs on regardless erapy or subs	st dose of stud of whether su sequent therap	ly drug until ubject is on Py	24-hour urine sample can be collected within \pm 7 days of visit, and must be obtained in all subjects		

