8.3 Endpoints

8.3.1 Primary Endpoint(s)

8.3.1.1 EPd Cohort

PFS is defined as the time from first dosing date to the date of the first documented progression per IMWG uniform criteria or death due to any cause, whichever occurs first. Subjects who die without a reported prior progression will be considered to have progressed on the date of their death. Subjects who did not progress or die will be censored on the date of their last evaluable assessment. Subjects who did not have any on study efficacy assessments and did not die will be censored on the first dosing date.

Subjects who switched to subsequent therapy prior to documented progression will be censored on the date of the last evaluable assessment prior to the initiation of the new therapy.

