4.1.3 Primary Definition of Progression-Free Survival

Progression Free Survival (PFS) is defined as the time from first dosing date to the date of the first documented progression per IMWG uniform criteria or death due to any cause, whichever occurs first. Subjects who die without a reported prior progression will be considered to have progressed on the date of their death. Subjects who did not progress or die will be censored on the date of their last adequate tumor assessment. Subjects who did not have any on study efficacy assessments and did not die will be censored on the first dosing date.

Subjects who switched to subsequent therapy prior to documented progression will be censored on the date of the last adequate tumor assessment prior to the initiation of the new therapy.

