4.1.4 Secondary Definition of Progression-Free Survival

Progression Free Survival (PFS) is defined as the time from first dosing date to the date of the first documented tumor progression per IMWG uniform criteria or death due to any cause, whichever occurs first. Subjects who die without a reported prior progression will be considered to have progressed on the date of their death. Subjects who did not progress or die will be censored on the date of their last adequate tumor assessment. Subjects who did not have any on study efficacy assessments and did not die will be censored on the first dosing date.

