7.5 Efficacy

7.5.1 Progression-Free Survival

The primary analysis of this study is to estimate the two definitions of progression free survival (PFS) in all treated patients. The median PFS and 2-sided 95% confidence interval will be caculated via Kaplan-Meier (KM) estimation procedure. The PFS function will be estimated using the KM product limit method and will be displayed graphically. Estimates for 1-year, 2-year, and 3-year PFS rates will be presented along with their associated 95% CIs. These estimates will be come from the KM curve and their standard errors (SEs), for use in constructing CIs, will be computed using Greenwood's formula¹⁷ and on log-log transformation applied on the survivor function.

Analyses of PFS will be conducted based on all treated population, and also by subgroups based on lines of prior therapy (2L/3L groups), or by age group (<65 years, \geq 65 years), and (<75 years, \geq 75 years). Subgroup analysis by ECOG PS (0-1,2), by response to most recent line of therapy (relapsed and refractory, relapsed, refractory, intolerant) and by ISS stage (I,II,III) if albumin and beta 2 microglobulin data are available will be conducted as well. PFS is also evaluated based on 3 levels of response (VGPR or better, PR, SD or MR). PFS will be estimated using the Kaplan-Meier (KM) product limit method and presented using a KM curve.

Time from last tumor assessment to data cut-off in months will be summarized by treatment arm and overall for all treated subjects. Subjects who have a PFS event will be considered as current for this analysis.

A by-subject listing will be presented including PFS duration on all treated population, whether the subject was censored, and if censored, the reason.

All of the analyses will be repreated for primary and secondary definitions of PFS.

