	• Development of hypercalcemia (corrected serum calcium > 11.5 mg/100 mL) that can be attributed solely to the plasma cell proliferative disorder

Table 7:DEFINITIONS OF RESPONSE AND PROGRESSION CRITERIA
(MODIFIED FROM IMWG)

^a All response categories require 2 consecutive assessments made at any time before the institution of any new therapy; all categories also require no known evidence of progressive or new bone lesions if radiographic studies were performed. Radiographic studies are not required to satisfy these response requirements. Bone marrow assessments need not be confirmed.

^b Note clarification to IMWG criteria for coding CR and VGPR in patients in whom the only measurable disease is by serum FLC levels: CR in such patients is defined as a normal FLC ratio of 0.26-1.65 in addition to CR criteria listed above. VGPR in such patients is defined as a > 90% decrease in the difference between involved and uninvolved FLC levels.

^c Presence or absence of clonal cells is based upon the κ/λ ratio. An abnormal κ/λ ratio by immunohistochemistry and/or immunofluorescence requires a minimum of 100 plasma cells for analysis. An abnormal ratio reflecting presence of an abnormal clone is κ/λ of > 4:1 or < 1:2.

^d For progressive disease, serum M-component increase of ≥ 1 g/dL is sufficient to define progression if starting M-component is ≥ 5 g/dL

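### EN progression must be confirmed before new therapy, yet PFS is censored at a switch before documented progression, so one PD followed by new therapy is lost as an event; whether EPd is affected is ambiguous

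*SAP*

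**What the plan says.** **Censoring.** SAP 4.1.3, which is not specific to a cohort, says: "Subjects who switched to subsequent therapy prior to documented progression will be censored on the date of the last adequate tumor assessment". Protocol 8.3.1.1 has the same rule for EPd: "Subjects who switched to subsequent therapy prior to documented progression will be censored on the date of the last evaluable assessment prior to the initiation". Protocol 8.3.2.2 applies it to EN by cross-reference.

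**Confirmation in EN.** The response rows of Protocol Tables 5.1-4 and 5.1-5 say: "Response assessments and PD require confirmation (2 consecutive assessments made at any time) before the institution of any new therapy". Table 5.1-6 (Cycle 5 onward) also names PD next to responses of PR or better.

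**Confirmation in EPd.** Tables 5.1-2 and 5.1-3 contain no general confirmation rule for PD. Table 5.1-3 asks for a second value only for corrected calcium: "if used as criterion for disease progression, must be confirmed by second value".

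**General text.** Footnote a of SAP Appendix 3, repeated in Protocol Appendix 4 and in substance in Protocol 5.4.4, says: "All response categories require 2 consecutive assessments made at any time before the institution of any new therapy". PD is a row of the table that carries this footnote, but the footnote does not name PD. It adds: "Bone marrow assessments need not be confirmed".

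**Second PFS definition.** SAP 4.1.4 omits the new-therapy sentence and counts the "first documented tumor progression per IMWG uniform criteria or death due to any cause, whichever occurs first". SAP 7.5.1 reports both: "The primary analysis of this study is to estimate the two definitions of progression free survival (PFS) in all treated patients".

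Neither SAP 4.1.3 nor 4.1.4 says how to code a PD assessment that is never repeated.

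**The concern.** Protocol 3.5 stops study drug at PD, and response is assessed every 4 weeks. Under SAP 6.1, continued 4-weekly assessment after stopping treatment is for subjects who stopped for a reason other than progression. The plan therefore does not clearly secure a second assessment for a subject taken off treatment at a first PD, and some subjects will start their next treatment without one.

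Where PD needs confirmation, such a subject has no documented progression when the new therapy starts and is censored. Kaplan-Meier estimation assumes that censored subjects have the same outlook as those still at risk. Here they are censored because they have just progressed, so events leave the numerator and the median moves up.

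The defect is plain for EN PFS, a secondary endpoint. If the EPd primary endpoint were coded the same way, the bias would sit in a median that the plan sizes against an 11-month historical figure.

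**Working it through.** **1. The plan's own EPd figures.** Inputs from SAP 5.1 and Protocol 8.1.1: 60 subjects, 24 months' accrual, 24 months' further follow-up, hazard λ = 0.0462 per month, medians of 11 and 15 months, one-sided 0.05.
- Events: 60 × [1 − (e^(−24λ) − e^(−48λ)) / (24λ)] = 60 × [1 − (0.330 − 0.109) / 1.109] = 48.0. The plan says 48.
- Power at 48 events: 0.710 from the one-sample exponential test, P(χ²₉₆ > (11/15) × χ²₉₆;₀.₉₅), and 0.693 from the one-sample log-rank, Φ(√48 × ln(15/11) − 1.645). The plan says about 70%.

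The planning model reproduces and serves below as the scale for size.

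**2. EN, rules applied in order.**
- Visit k meets a PD criterion. The schedule requires a second consecutive assessment before new therapy.
- New therapy starts first, so PD was not confirmed as required and the switch precedes documented progression.
- SAP 4.1.3 then censors at the last adequate assessment. SAP 4.1.1 defines adequacy by which laboratory results are present, so that can be visit k itself. The same section allows censoring at a visit only if progression can be ruled out there, which may push the date back one visit. Either way, the PD caused the censoring.

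**3. EPd, two readings.**
- Footnote a covers PD: the result is as in EN.
- Footnote a covers responses only: one qualifying PD is an event, apart from calcium, and there is no problem.

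For the first reading: PD is a row of the table, and Protocol 5.4.4 is headed for both response and progression. For the second: the footnote also requires every category to be free of progressive or new bone lesions, although new bone lesions are themselves a PD criterion; the EN schedules name PD separately from response; and the EPd schedules ask for a second value only for calcium. The text does not settle it.

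**4. The secondary definition.** SAP 4.1.4 removes the new-therapy censoring but relies on the same unspecified documented progression. Where confirmation is required, the single PD is not an event there either. The subject has a later event, on the next therapy or at death, or is censored later.

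**5. Size.** Let q be the share of PDs followed by new therapy without confirmation. It is not in the documents, so a range is used. Assume exponential PFS and 10% of events as deaths, which are never lost. A share 0.9q of events is then censored when it occurs, the estimated hazard is λ(1 − 0.9q), and the median is multiplied by 1/(1 − 0.9q).

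| q | Factor | True 15 months reads | True 11 months reads | Events by month 48, true 15 |
|---|---|---|---|---|
| 10% | 1/0.91 = 1.10 | 16.5 | 12.1 | 48.0 × 0.91 = 43.7 |
| 20% | 1/0.82 = 1.22 | 18.3 | 13.4 | 48.0 × 0.82 = 39.4 |
| 30% | 1/0.73 = 1.37 | 20.5 | 15.1 | 48.0 × 0.73 = 35.0 |

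For 11 months to read as 15: 1 − 0.9q = 11/15, so q = (4/15)/0.9 = 29.6%.

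A simulation (60 subjects, 28-day visits, cut at month 48, 15% of events as deaths, 2,000 runs) gave typical medians of 14.7 months with none lost and 16.6, 18.4 and 20.2 at q = 10, 20 and 30%. The formula with 15% deaths gives 15/(1 − 0.85q) = 16.4, 18.1 and 20.1. Simulated PDs fall on steps of 28/30.4375 = 0.92 month, so the formula is the cleaner measure.

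The 11- and 15-month columns and the event counts use EPd planning values. The documents give no planning median for EN PFS, so only the factor carries over to that cohort.

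**The case against.** The strongest case is that the plan's main result is untouched.

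- **Footnote a does not fit PD.** Its bone-lesion clause would bar skeletal progression from ever counting as PD. This is a good argument and may well be the intended reading. It does not remove the ambiguity, because the footnote sits on a table with a PD row and the SAP never says whether one PD is enough.
- **EN PFS is secondary.** It has no hypothesis and no historical benchmark. True, and this limits the consequences. The stated EN rules still give a biased estimate.
- **Confirmation can be quick.** The second assessment may be made at any time before new therapy, so it need not wait 4 weeks, and Protocol 3.5 stops study drug without requiring immediate new therapy. Bone marrow findings need no confirmation. These points lower q; they do not make it zero or say how the remaining cases are coded.
- **SAP 4.1.4 is reported alongside.** A wide gap between the two results would expose heavy new-therapy censoring. It would not restore the lost PD dates.

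Two stronger readings are tempting. A reader might infer that the EPd primary median is inflated; the documents support that only under one of two readings of footnote a. A reader might also infer from a factor of 1/(1 − q) that losing 27% of PDs turns 11 months into 15. That figure, 1 − 11/15, is a share of all events; with 10% deaths it corresponds to about 30% of PDs. No document supports a share of that size.

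**Conclusion.** The point holds for EN: confirmation before new therapy, combined with censoring at a switch before documented progression, makes some censoring event-driven and can bias the secondary PFS median upward. For EPd it is an unresolved ambiguity about what counts as a primary-endpoint event, not a demonstrated bias. Under the inclusive reading, the 48-event trigger for the EPd analysis would also be reached later.

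The direction is clear where confirmation applies. The size is conditional: about 10% on the median if one PD in ten is affected and about 37% if three in ten are, given exponential PFS and 10% of events as deaths. The true share is unknown. The secondary definition is a partial remedy.

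**What to change.** In SAP 4.1.3 and 4.1.4:

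1. State for each cohort whether PD needs confirmation. Reconcile the EPd and EN schedules, Protocol 5.4.4 and footnote a, including the calcium and bone marrow provisions.
2. Date PD at the first of its assessments.
3. Count a PD assessment that is not repeated because of new therapy, death or no further assessment as an event on that first PD date.
4. Do not count a PD assessment that is followed by a non-PD assessment.
5. Keep strictly confirmed PD as a sensitivity analysis, and report by cohort how many subjects had an unconfirmed PD followed by new therapy.

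The cost is a few sentences in the SAP, matching wording in the protocol tables, one sensitivity analysis and one count. The downside is that a few PDs due to laboratory noise will count as events, so the reported median may be slightly shorter.

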4.1.4 Secondary Definition of Progression-Free Survival

Progression Free Survival (PFS) is defined as the time from first dosing date to the date of the first documented tumor progression per IMWG uniform criteria or death due to any cause, whichever occurs first. Subjects who die without a reported prior progression will be considered to have progressed on the date of their death. Subjects who did not progress or die will be censored on the date of their last adequate tumor assessment. Subjects who did not have any on study efficacy assessments and did not die will be censored on the first dosing date.

4.2 Objective Response Rate (ORR)

The best overall response is determined as the best assessment based on all on-study efficacy data for the subject. Overall Response Rate (ORR) is defined as proportion of subjects with a best overall response of partial response (PR) or better.

4.3 Overall Survival (OS)

Overall Survival (OS) is defined as the time from first dosing date to the date of death from any cause. A subject who has not died will be censored at last known date alive.

4.6 Safety and Tolerability

Safety and tolerability endpoints consist of all deaths, AEs, drug-related AEs, AEs leading to treatment discontinuation, SAEs, and drug-related SAEs and specific laboratory abnormalitites (worst grade) collected during the treatment and up to 60 days after discontinuation of study drug will be tabulated using worst grade per NCI CTCAE v3.0 criteria by system organ class and MedDRA preferred term.

5 SAMPLE SIZE AND POWER

5.1 EPd Cohort

Seventy-two subjects will be screened with approximately 17% projected to fail screening. This total number is based on logistical consideration with statistical properties outlined below. Screening will continue until a minimum of 60 subjects are enrolled and treated.

Under the assumptions that:

- progression-free survival is exponentially distributed
- median time of progression-free survival is 11 months for subjects treated with pomalidomide + dexamethasone and will increase to median of 15 months with the addition of elotuzumab to the treatment mix;
- an increase of 4 months in median corresponds to relative risk ratio of 0.73 (0.0462 monthly risk in the elotuzumab add-on and 0.0630 monthly historical risk in the pomalidomide + dexamethasone treated-subjects)

60 subjects enrolled over a 24-month period are sufficient to detect an increase in median from 11 to 15 months with about 70% power in a one-sided test with a 0.05 significance level.

Assuming a monthly hazard rate of 0.0462, 48 of the 60 treated subjects are **expected** to have PFS events over a 24-month follow up period.

Power is calculated using PASS12 using the one-sample exponential module where the median is mapped to mean by dividing the assumed alternative median by logarithm of 2. The calculated power and event counts are consistent with power and event counts based on one sample log rank test where the number of events is calculated assuming relative risk ratio of 0.73.

5.2 EN Cohort

The planned sample size will be approximately 30 treated subjects; screening will continue until a minimum of 30 patients are enrolled and treated.

For a 30% observed ORR rate and a sample size of N=30 yields an exact confidence interval of [0.15, 0.49]. These design parameters ensure a lower bound higher than 15%.

6 STUDY PERIODS, TREATMENT REGIMENS AND POPULATIONS FOR ANALYSES

6.1 Study Periods

There are three periods in this study: screening, on-treatment and post-treatment follow-up.

Screening: Most screening procedures must be done no more than 14 days prior to first dose of treatment. Some exceptions include Serum β 2-microglobulin, Pregnancy Test, Myeloma Urine and Serum Lab tests, Bone Marrow Aspiration/Biopsy, Skeletal Imaging, CT/MRI assessment for extramedullary soft tissue plasmacytoma, which can be done up to 60 days prior to first dose of study drug. See Section 5 of the Protocol for full details of study procedures and timings. For

analyses purposes data collected on or after information consent date and prior to first dose will fall into the screening/baseline period.

Baseline: Baseline evaluations will be those performed within 60 days prior to first dosing date. When an assessment is repeated multiple times within the screening period, the baseline evaluation will be the one closest to the first dosing date.

All laboratory tests and procedures done on the first date of dosing will be assumed to have occurred prior to dosing and therefore baseline evaluation for those parameters will be those prior or on the first dosing date.

On-Treatment Period: In the post baseline period, every 28 days is defined as a cycle. AEs will be defined as AEs with an onset date-time on or after the date-time of the first dose of study treatment (or with an onset date on or after the day of first dose of study treatment if time is not collected or is missing) and within 60 days of the last dose of study treatment. Subjects should have myeloma urine and serum laboratory assessments, and the tumor response assessments per IMWG uniform criteria will be every 4 weeks from date of first dose of study drug on Cycle 1 Day 1 until progression or discontinuation. Study treatment ends when the subject progresses, experiences unacceptable toxicity, or withdraws consent.

Follow-up Period: Subjects who are discontinued from further study treatment for reasons other than progression will be followed every 4 weeks for disease progression. Following disease progression, subjects will be followed at least annually for survival until the subject dies or the study ends.

